### 10.1.8.2 STUDY RECORDS RETENTION

Study documents and de-identified individual data will be retained for 25 years after the completion of the data collection period. This time period of retention is in accordance with the requirements of the IRB. No records will be destroyed without the written consent of the IRB. It is the responsibility of the investigator-sponsor destroy these documents when they are no longer required to be retained.

---

## 10.1.9 PROTOCOL DEVIATIONS

A protocol deviation is any noncompliance with the clinical trial protocol or International Conference on Harmonization Good Clinical Practice (ICH GCP). The noncompliance may be either on the part of the participant or the investigators. As a result of deviations, corrective actions are to be developed by the site and implemented promptly.

These practices are consistent with ICH GCP:

- 4.5 Compliance with Protocol, sections 4.5.1, 4.5.2, and 4.5.3
- 5.1 Quality Assurance and Quality Control, section 5.1.1
- 5.20 Noncompliance, sections 5.20.1, and 5.20.2.

It is the responsibility of the site investigator to use continuous vigilance to identify and record deviations within 2 working days of identification of the protocol deviation, or within 2 working days of the scheduled protocol-required activity. All deviations must be addressed in study documents.

---

## 10.1.10 PUBLICATION AND DATA SHARING POLICY

This study will be conducted in accordance with the following publication and data sharing policies and regulations:

National Institutes of Health (NIH) Public Access Policy. It requires scientists to submit final peer-reviewed journal manuscripts to the digital archive [PubMed Central](#) upon acceptance for publication.

This study will comply with the NIH Data Sharing Policy and Policy on the Dissemination of NIH-Funded Clinical Trial Information and the Clinical Trials Registration and Results Information Submission rule. As such, this trial will be registered at [ClinicalTrials.gov](#), and results information from this trial will be submitted to [ClinicalTrials.gov](#). In addition, every attempt will be made to publish results in peer-reviewed journals. Data from this study may be requested from other researchers 25 years after the completion of the primary endpoint by contacting [name].

#### 10.1.11 CONFLICT OF INTEREST POLICY

The independence of this study from any actual or perceived influence, such as by the cannabis industry, is critical. Therefore, any actual conflict of interest of persons who have a role in the design, conduct, analysis, publication, or any aspect of this trial will be disclosed and managed. Furthermore, persons who have a perceived conflict of interest will be required to have such conflicts managed in a way that is appropriate to their participation in the design and conduct of this trial. The study leadership in conjunction with the University of Guelph has established policies and procedures for all study group members to disclose all conflicts of interest and will establish a mechanism for the management of all reported dualities of interest.

#### 10.2 ADDITIONAL CONSIDERATIONS

N/A

#### 10.3 ABBREVIATIONS

AE	Adverse Event
ANCOVA	Analysis of Covariance
CRF	Case Report Form
FDA	Food and Drug Administration
FDAAA	Food and Drug Administration Amendments Act of 2007
GCP	Good Clinical Practice
IB	Investigator's Brochure
ICH	International Conference on Harmonisation
IRB	Institutional Review Board
ISM	Independent Safety Monitor
ITT	Intention-To-Treat
MedDRA	Medical Dictionary for Regulatory Activities
MSDS	Material Safety Data Sheet
NIH	National Institutes of Health
PI	Principal Investigator
QA	Quality Assurance
QC	Quality Control
SAE	Serious Adverse Event
SAP	Statistical Analysis Plan

SOA	Schedule of Activities
SOC	System Organ Class
SOP	Standard Operating Procedure
UP	Unanticipated Problem

## 1. STATISTICAL CONSIDERATIONS

### 1. STATISTICAL HYPOTHESES

- Primary Efficacy Endpoint(s):
  1. Pulse Wave Velocity will be increased following exercise, smoking high THC cannabis, and vaporizing high THC cannabis relative to resting baseline; effects of cannabis consumption and exercise are likely to be additive. Vaporizing high CBD cannabis will not increase pulse wave velocity.
  2. Percent flow mediated dilation will be decreased following exercise and smoking high THC cannabis; effects are likely to be additive. Vaporizing both high THC and high CBD cannabis will not decrease percent flow mediated dilation.
  3. Ejection fraction will be decreased following smoking and vaporizing high THC cannabis. Exercise and vaporization of high CBD cannabis will not be associated with reductions in ejection fraction.
  4. E/A Ratio will be decreased following high THC cannabis smoking only.
  5. Myocardial strain will be decreased following high THC cannabis smoking and vaporizing only.
  6. Myocardial twist will be decreased following high THC cannabis smoking and vaporizing only.
  7. Burst Frequency will be increased following high THC cannabis only.
  8. Burst Incidence will be increased following high THC cannabis only.
- Secondary Efficacy Endpoint(s):
  1. Systolic Blood Pressure will be increased following cannabis consumption and will be decreased following all bouts of exercise.
  2. Diastolic blood pressure will be unchanged under all conditions
  3. Heart rate will be increased following cannabis consumption and exercise.
  4. Stroke volume will be increased with exercise, and will be reduced following cannabis consumptions. These competing effects will result in an attenuation of increases in stroke volume when exercise is preceded by cannabis consumption.
  5. Cardiac output will be unchanged under all conditions
  6. Work completed will be reduced when preceded by cannabis consumption of all forms
  7. Average power output will be reduced when preceded by cannabis consumption of all forms
  8. Oxygen consumption will be reduced when exercise is preceded by consumption of high THC cannabis
  9. Rating of Perceived Exertion will be increased following consumption of high THC cannabis
  10. Rate-pressure product will be increased during exercise, when the bout is preceded by cannabis consumption.

### 2. SAMPLE SIZE DETERMINATION

In accordance with our power calculation, 15 participants are required to have a power of at least 0.8 with an alpha of 0.05, for expected changes in measures of endothelial function (pilot work, change in FMD in response to exercise pre =  $4.8 \pm 2.5$  %, post =  $2.7 \pm 1.7$ %) (FMD in rats in response to cannabis smoke, pre =  $7.5 \pm 2.5$ %, post =  $2.4 \pm 1.4$  %), artery stiffness (pilot

work, change in PWV pre =  $7.4 \pm 1.3$  m/s, post (at rest) =  $6.0 \pm 1.3$  m/s) and cardiac function (pilot work, peak longitudinal strain: pre =  $-18.3 \pm 1.2$  %, post =  $-17.0 \pm 1.9$  %), therefore we will recruit 20 participants in each phase of the study to account for potential dropout.

### 3. POPULATIONS FOR ANALYSES

Only participants who complete all study procedures will be included for analysis of efficacy endpoints. All participants who consume cannabis at any time will be included in the analysis of safety endpoints.

### 4. STATISTICAL ANALYSES

#### 1. GENERAL APPROACH

Our study will be divided into two phases each of which will be analyzed independently. All tests of significance will be two-tailed, and statistical significance will be based upon an alpha error probability of 5% and a power for 80%. The data will be evaluated using both parametric and non-parametric tests, as applicable. If the data are found to be not normally distributed, the raw data will be transformed using an appropriate transformation model in order to perform the parametric assessments. Non-parametric tests will be performed on raw data. The data will be assessed as continuous and will be presented as means with standard deviations. A one-way analysis of covariance will be used to assess the treatment effects (Phase I: exercise, vaporizing THC, smoking THC, vaporizing + exercise THC, smoking THC + Exercise, Phase II: exercise, vaporizing THC, vaporizing CBD, vaporizing + exercise THC, Vaporizing CBD + Exercise) on the primary endpoints. Covariates will be introduced into the models in order to assess the impact of certain potential factors on outcome, including fitness, blood pressure, resting heart rate, and any other factors that are observed during the study that appear to potentially influence the outcome.

Our secondary endpoints will be assessed using a repeated measures one-way ANOVA and paired t-tests. If there are significant interactions differences between pairs of means will be determined with a Bonferroni post-hoc test.

#### 2. ANALYSIS OF THE PRIMARY EFFICACY ENDPOINT(S)

All primary endpoints will be measured as continuous variables and will be repeated after each intervention performed on a given study visit. A one-way ANCOVA will be used to assess treatment effects. Covariates will include basic cardiovascular and haemodynamic variables that may confound primary endpoints. These covariates include heart rate, blood pressure, and pulse wave velocity. Results will be presented as adjusted means with standard deviations. Primary endpoints will only be analyzed for participants who complete the entirety of at least one phase of the proposed study. Missing data will be imputed using mean imputation from all other measurements collected from the given participant. Outliers will be included and excluded in independent analysis, both of which will be reported.

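### The primary one-way ANCOVA applies one residual variance to repeated rest and exercise measurements, so the smoke-versus-vapour and THC-versus-CBD standard errors are miscalibrated

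*SAP*

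**What the plan says.** SAP 4.2 and protocol 9.4.2 give the primary analysis in one sentence: "A one-way ANCOVA will be used to assess treatment effects". SAP 4.1 lists the conditions that enter it. The first list reads "Phase I: exercise, vaporizing THC, smoking THC, vaporizing + exercise THC, smoking THC + Exercise". The second phase has the same layout, with the vaporized high-CBD product in place of smoking.

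Each phase thus has two rest conditions and three exercise conditions. Protocol 4.1 states that every participant completes every condition.

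The SAP mentions no participant term, no check of equal variances and no method for unequal variances. Its remedies for failed assumptions are transformation when data are not normal, and non-parametric tests that it does not specify. It does not list the primary contrasts. For the secondary endpoints it does recognise the repeated measures: "Our secondary endpoints will be assessed using a repeated measures one-way ANOVA and paired t-tests".

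The sample-size section (SAP 2) gives pilot SDs before and after exposure, including one pair described as "change in FMD in response to exercise pre" and post.

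**The concern.** The questions in protocol 4.1 are comparisons within a state: smoking against vaporizing in Phase I, and high THC against high CBD in Phase II, each at rest and with exercise. A one-way ANCOVA tests all of these against one residual variance averaged over the five conditions. Two things can make that variance wrong for a given contrast.

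- It includes the between-participant variation, which cancels from a within-participant difference.
- It averages over rest and exercise even if one state is noisier.

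If either applies, the same true effect can be declared or missed depending on the state in which it is tested. The natural repair is to borrow the repeated-measures ANOVA already planned for the secondary endpoints. That removes the first fault and leaves the second, so the error structure needs to be settled in the same edit.

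**Working it through.** **Inputs from the documents.** Two-sided tests ("All tests of significance will be two-tailed"). Sample size: "15 participants are required to have a power of at least 0.8 with an alpha of 0.05". Pilot figures from SAP 2:

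- FMD before and after exercise: 4.8 ± 2.5 and 2.7 ± 1.7
- PWV before and after, at rest: 7.4 ± 1.3 and 6.0 ± 1.3
- Longitudinal strain before and after, state not given: -18.3 ± 1.2 and -17.0 ± 1.9
- Rat FMD before and after smoke, no exercise: 7.5 ± 2.5 and 2.4 ± 1.4

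**Assumed.** A common within-participant correlation r, which the documents do not give (0 to 0.7 in the simulations). SD 2.5 for every rest condition and 1.7 for every exercise condition. No covariates.

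**The plan's own figure.** With a paired t-test, SD of the difference = sqrt(s1² + s2² - 2·r·s1·s2). At r = 0.5, strain gives sqrt(1.44 + 3.61 - 2.28) = 1.664 for a change of 1.3, which needs 15 participants (power 0.803). FMD needs 11 and PWV 9. So the plan's 15 is reproduced by a paired calculation at r = 0.5.

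**Model as written.** Pooled variance = (2 × 2.5² + 3 × 1.7²)/5 = (12.50 + 8.67)/5 = 4.234, SD 2.06. Model SE divided by true SE for a contrast between two conditions of SD s is 2.06/(s·sqrt(1 - r)).

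- r = 0: rest 2.06/2.5 = 0.82 (18% too small); exercise 2.06/1.7 = 1.21 (21% too large)
- r = 0.5: rest 1.16; exercise 1.71 (both too large)
- The rest ratio equals 1 when 1 - r = 4.234/6.25, that is r = 0.32

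**Participant term added, one pooled error kept, r = 0.5.** Sum of variances = 21.17. Sum of all entries of the covariance matrix = 0.5 × 21.17 + 0.5 × (2 × 2.5 + 3 × 1.7)² = 10.585 + 51.005 = 61.59. Expected error mean square = (21.17 - 61.59/5)/4 = 2.213. The contrasts need 6.25 × 0.5 = 3.125 (rest) and 2.89 × 0.5 = 1.445 (exercise). SE ratios are sqrt(2.213/3.125) = 0.84 and sqrt(2.213/1.445) = 1.24.

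**Simulated false-positive rates**, n = 15, nominal 5%, 40,000 runs (rest contrast / exercise contrast):

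| r | One-way, as written | Participant term, pooled error | Paired error per contrast |
|---|---|---|---|
| 0 | 10.9% / 1.8% | 10.9% / 1.8% | 5.3% / 4.8% |
| 0.3 | 5.5% / 0.6% | 10.1% / 1.8% | 5.0% / 5.2% |
| 0.5 | 2.6% / 0.2% | about 9.8% / 1.8% | 5.0% / 5.0% |
| 0.7 | 0.6% / below 0.1% | 9.0% / 1.4% | 5.2% / 4.9% |

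At n = 20 the pattern is the same: 2.5% / 0.1% as written and 10.0% / 1.6% with a participant term, at r = 0.5.

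**Power.** For an FMD exercise contrast of 1.05 points (half of the 2.1-point pilot change) at n = 15 and r = 0.5: 18% as written, 47% with a participant term and pooled error, 60% with the paired error.

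**Equal SDs.** With the PWV values (1.3 and 1.3) and r = 0.5, the model as written gives about 0.8% for both contrasts. A participant term with pooled error gives 5.0% and 5.1%, so there the participant term is enough.

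**The case against.** A reader might infer that the plan's errors are too small in one state and too large in the other. For the model as written, that needs r below about 0.32 with the FMD figures. Protocol 4.2 justifies the design by large variation between people, and the plan's N is reproduced at r = 0.5, where both standard errors are too wide. The 9 to 10% rest figures at r = 0.3 or more belong to a partly repaired model that the SAP does not specify. This stands.

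A reader might also infer that the pilot SDs differ between rest and exercise in general. They do not show that.

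- PWV SDs are equal.
- The state of the post-exposure strain value is not given, and protocol 8.1 places echocardiography before exercise at the control visit. Strain should not be cited as rest/exercise evidence.
- The FMD value of 2.5 is a pre-exposure baseline, whereas the modelled rest conditions follow cannabis. If the rat post-smoke SD of 1.4 stood for them, the asymmetry would reverse: about 2.6% at rest and 6.4% with exercise, with a participant term at r = 0.5.
- The FMD variance ratio of 2.16 may be noise. If the pilot had 15 participants (an assumption), a rough two-sided F limit for 14 and 14 df is 2.98.
- Residual SDs after the planned covariates are unknown.

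These points stand and leave the direction open. They do not support a common variance either, and they do not touch the omission of repeated measures.

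Extending the point with equal force to the secondary endpoints is not supported. Paired t-tests, which carry their own error, are already planned there, and the SAP does not say that the Bonferroni comparisons use a pooled mean square.

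**Conclusion.** The point holds in this form: the primary model gives miscalibrated standard errors for the within-state contrasts, because it ignores the repeated measures and assumes one variance over rest and exercise. With the FMD pilot SDs and n = 15, the error rates run from 10.9% and 1.8% (rest, exercise) at r = 0 to 2.6% and 0.2% at r = 0.5. A participant term alone does not restore 5% if variances differ as in that pilot.

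The sizes rest on an assumed r, raw pilot SDs from a pilot of unstated size, the pre-exercise SD standing for post-cannabis rest, and no covariates. The documents do not establish that the errors run in opposite directions under the model as written, nor which state is noisier. What does not depend on those assumptions is the remedy: contrasts tested with their own paired error stayed near 5% in every setting tried. The change is worth making before analysis. Confidence in the exact figures is moderate at best.

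**What to change.** In SAP 4.2 and protocol 9.4.2, replace the one-way ANCOVA by named within-participant contrasts: smoke versus vapour (Phase I) and THC versus CBD (Phase II), each at rest and after exercise. Test each with the error of its own paired difference. An alternative is a mixed model with a participant effect, a participant-by-exercise effect and separate residual variances for rest and exercise. It is similar to the paired test but not identical, because it pools the exercise conditions.

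Minor addition in SAP 4.3 and protocol 9.4.3: apply a Greenhouse-Geisser correction to the repeated-measures ANOVA, and use the paired t-tests already planned for the post-hoc comparisons.

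Cost: some SAP wording and a few lines of code. At n = 15 the paired version has 15 - 1 = 14 error df per contrast, against 4 × 14 = 56 for a pooled error with a participant term. If variances are in fact equal, that loses about 4 to 5 points of power; for example 65% becomes 61% for a 1.05-point contrast with SD 1.7 throughout and r = 0.5.

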#### 3. ANALYSIS OF THE SECONDARY ENDPOINT(S)

Analysis of secondary endpoints will be independent of analysis of primary endpoints. All secondary endpoints will be measured as continuous variables and will be reported as adjusted

means with standard deviations. Repeated measures one-way ANOVA and paired Student's *t*-tests will be used for analyses. If there are significant interactions differences between pairs of means will be determined with a Bonferroni *post-hoc* test. Missing data will be imputed using mean imputation from all other measurements collected from the given participant. Outliers will be included and excluded in independent analysis, both of which will be reported.

---

#### 4. SAFETY ANALYSES

Safety analysis will be performed using summary statistics during treatment interventions. Adverse events will be coded according to the Medical Dictionary for Regulatory Activities and will have severity, and relationship of adverse event to study intervention presented by System Organ Class and preferred term groupings. Each instance of an adverse event will be presented as a discrete event. Duration of events, severity, relationship to intervention, expectation, and outcome will be presented. Adverse events that lead to premature discontinuation will be presented in a table, along with all treatment-emergent serious adverse events.

---

#### 5. BASELINE DESCRIPTIVE STATISTICS

Baseline characteristics of participants will be presented in a table. No descriptive statistics other than mean and standard deviation will be presented as the proposed study uses a within-subjects design.

---

#### 6. PLANNED INTERIM ANALYSES

No interim analysis is planned for the proposed study. *Phase I* of this study will be completed in advance of *phase II*, and as such efficacy and safety analyses for *phase I* may occur before the completion of *phase II*. The results of *phase I* will not be used to modify the desired sample size or planned analyses of *phase II*.

---

#### 7. SUB-GROUP ANALYSES

Sub-analysis of each primary and secondary endpoint will be performed based upon sex. This analysis will be performed identically to all efficacy and safety analyses with the only adjustment being the exclusion of the sex not of interest.

---

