Continuous blood pressure, heart rate, and electrocardiogram monitoring will occur prior to, and during cannabis administration (prior to exercise) on all visits where cannabis is consumed. This procedure will be followed throughout the entirety of the 40-minute cannabis consumption period. If either systolic or diastolic blood pressure exceeds 160mmHg or 90mmHg at rest, respectively, exercise will not be performed, and the study visit will not continue. If heart rate exceeds 100bpm or falls below 40bpm at rest, exercise will not be performed, and the study visit will not continue.

All research will be performed within the department of Human Health and Nutritional Sciences at the University of Guelph.

There are no planned interim analyses planned for the current trial.

A sub-group analysis will be performed, with participants divided by sex, to determine the existence of any sex differences in primary and secondary endpoints.

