## 5.5 STRATEGIES FOR RECRUITMENT AND RETENTION

We seek to recruit 20 individuals per phase, 10 of which will be female and 10 of which will be male. Participants will be recruited from the community in Guelph, Ontario. In line with our IRB approved methods, recruitment posters will be posted at the University of Guelph and around the city. A social media posting will be sent via Twitter from the official Human Performance and Health Research Laboratory account. Additionally, the study poster will be presented to students in undergraduate lectures at the University of Guelph. Participants may also be recruited by word of mouth. Each participant who completes a session of microneurography will be compensated \$100 CAD in line with typical institutional procedures.

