### 7.2 PARTICIPANT DISCONTINUATION/WITHDRAWAL FROM THE STUDY

Participants are free to withdraw from participation in the study at any time upon request. This includes during the inhalation procedure.

If a participant wishes to withdraw during or after the inhalation of cannabis they will be required to remain in the laboratory for the requisite recovery period of 4 hours. Each hour subjective effects, heart rate, and blood pressure will be measured.

An investigator may discontinue or withdraw a participant from the study for the following reasons:

- Pregnancy
- If any severe adverse event (AE), or other medical condition or situation occurs such that continued participation in the study would not be in the best interest of the participant
- If the participant reports meeting an exclusion criterion (either newly developed or not previously recognized) that precludes further study participation
- Participant unable to complete study procedures

The reason for participant discontinuation or withdrawal from the study will be recorded. Participants who discontinue the study will be replaced to ensure that the required pre-determined statistical power is met.

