#### 9.4.7 SUB-GROUP ANALYSES

Sub-analysis of each primary and secondary endpoint will be performed based upon sex. This analysis will be performed identically to all efficacy and safety analyses with the only adjustment being the exclusion of the sex not of interest.

---

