#### 9. EXPLORATORY ANALYSES

There are no planned exploratory analyses in the current study.

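### The plan repeats each analysis within one sex, so it never tests or estimates the male-female difference it sets out to determine

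*SAP*

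**What the plan says.** - **Purpose.** Protocol 4.1 (Overall Design) divides participants by sex "to determine the existence of any sex differences in primary and secondary endpoints".
- **Method.** Protocol 9.4.7 and SAP 4.7 (Sub-Group Analyses) share the same text. The sex analysis covers each primary and secondary endpoint and is "performed identically to all efficacy and safety analyses", with "the only adjustment being the exclusion of the sex not of interest".
- **Models being repeated.** For the primary endpoints, SAP 4.1 (General Approach) states: "A one-way analysis of covariance will be used to assess the treatment" effects, over five conditions per phase. Secondary endpoints get a one-way repeated-measures ANOVA and paired t-tests. Neither model has a sex factor, and sex is not among the named covariates.
- **Numbers.** Protocol 5.5: "We seek to recruit 20 individuals per phase, 10 of which will be female and 10 of which will be male". SAP 2 (Sample Size Determination): "15 participants are required to have a power of at least 0.8 with an alpha of 0.05".
- **Other analyses.** SAP 4.9: "There are no planned exploratory analyses in the current study".

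**The concern.** Whether the sexes differ is a question about a contrast between men and women. An analysis that excludes one sex cannot contain that contrast. Running it twice gives two effects, each tested against zero, and no test or interval for the gap between them.

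This can mislead in two ways. If the sexes respond identically, one can be significant and the other not, simply because each half of the sample is small. If the sexes truly differ but both effects are significant, the difference can go unreported. The plan does not say how either pattern will be read, so it invites the comparison of two p-values.

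The sex question covers every primary and secondary endpoint, and recruitment is balanced by sex. The main treatment comparisons do not depend on it.

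**Working it through.** **1. Is there a between-sex comparison anywhere?**

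| Place | What it offers | Compares men with women? |
|---|---|---|
| Protocol 9.4.7 / SAP 4.7 | Same analyses, other sex excluded | No |
| SAP 4.1, 4.2 (primary) | One-way ANCOVA on condition | No |
| SAP 4.1, 4.3 (secondary) | One-way repeated-measures ANOVA, paired t-tests | No; the reference to interactions cannot mean sex-by-condition without a sex factor |
| SAP 4.1, open-ended covariate clause | Could at most add sex as a covariate | No; a main effect is not a difference in response |
| SAP 4.9 | No exploratory analyses | No |

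The finding rests on this table. The arithmetic below only illustrates its size.

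**2. Reproducing the plan's sample size.** Inputs from SAP 2, pre to post:
- exercise FMD: 4.8 (SD 2.5) to 2.7 (SD 1.7) %
- PWV: 7.4 (SD 1.3) to 6.0 (SD 1.3) m/s
- strain: -18.3 (SD 1.2) to -17.0 (SD 1.9) %

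SD of change = √(s₁² + s₂² − 2·r·s₁·s₂). The documents give no pre-post correlation r, so r is an assumption. With a paired t-test, two-sided alpha 0.05, 80% power and r = 0.5, the required n is 11 (FMD), 9 (PWV) and 15 (strain). The largest, 15, matches the plan.

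**3. Discordance without assuming r.** Solve one-sample t power = 0.80 at n = 15: the effect is d = 0.778 SD of change. Power for the same d at n = 10 is p = 0.593. If both sexes have this same effect, P(exactly one significant) = 2p(1 − p) = 2 × 0.593 × 0.407 = **0.48**. A simulation of 200,000 trials gave 48.1%, with a direct two-sample test falsely positive 5.0% of the time. With no effect in either sex, 2 × 0.05 × 0.95 = 0.095.

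**4. Discordance with the pilot effects, 10 per sex, equal true effects.**

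| Endpoint | Change / SD of change at r = 0.5 | Within-sex power | Exactly one significant, r = 0.5 | r = 0.3–0.7 | r = 0–0.8 |
|---|---|---|---|---|---|
| Strain | 1.3 / 1.664 = 0.781 | 0.60 | 48% | 36–50% | 23–50% |
| FMD (exercise) | 2.1 / 2.211 = 0.950 | 0.76 | 36% | 16–46% | 6–50% |
| PWV | 1.4 / 1.300 = 1.077 | 0.86 | 25% | 5–40% | 0.5–49% |

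**5. What a direct test can do.** Two-sample t-test on within-person change, 10 per sex, df = 18:
- power if a 0.778 SD effect is wholly absent in one sex: 38%
- difference detectable with 80% power: about 1.32 SD of change
- 95% CI half-width: t(0.975, 18) × √(2/10) = 2.101 × 0.447 = 0.94 SD
- participants for 80% power at 0.778 SD: about 27 per sex

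**The case against.** - **The percentages describe a reading the plan does not adopt.** Neither document says that significance in one sex only will be called a sex difference. This stands: 48%, 36% and 25% are rates for a likely misreading, not error rates of a stated rule. But the plan offers no other route from its method to its purpose.
- **The lead figure is close to its ceiling.** 2p(1 − p) cannot exceed 50%, and d = 0.778 corresponds to exactly 80% power, while the plan asks for at least 0.8. At r = 0.5 only strain sits there, and PWV falls to 5% at r = 0.7. This stands, and the size for FMD and PWV depends on r. All the figures use a plain paired t-test, whereas the primary analysis is an ANCOVA.
- **Sex-specific means will be reported, so the difference is one subtraction away.** True of a point estimate. The plan specifies neither that contrast nor its uncertainty.
- **Ten per sex is not assured.** Protocol 7.2 says: "Participants who discontinue the study will be replaced to ensure that the required pre-determined statistical power is met". The powered number is 15, replacements are not matched by sex, and efficacy analysis is restricted to completers, so 7 and 8 is also possible. Power at d = 0.778 is then 0.410 and 0.475, and discordance is 0.410 × 0.525 + 0.475 × 0.590 = 0.50. The point is unchanged.
- **A direct test is weak and would be repeated over many endpoints.** Both are true. With 8 primary and 10 secondary hypotheses, one independent 5% test each would give 1 − 0.95¹⁸ = 60% chance of at least one false positive. This argues for estimates with intervals, named contrasts and an exploratory label. It does not make within-sex p-values a substitute.
- **Sex is in neither the objectives nor the hypotheses.** Correct, and it limits the weight of the point.

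**Conclusion.** The concern holds. It follows from setting Protocol 4.1 beside Protocol 9.4.7 and SAP 4.7: the stated method cannot answer the stated question, and nothing elsewhere in the plan does.

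The likely size is material but illustrative. Identical responses would give one significant and one non-significant sex about 48% of the time for an effect powered at exactly 80% with n = 15. For the pilot effects at an assumed r = 0.5, the figures are 25–48%. They assume a paired t-test, two-sided alpha 0.05, 10 per sex and the same SD of change in both sexes. The problem is clearest for strain and depends on r for FMD and PWV.

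The plan should be changed on this point, but it does not threaten the main treatment comparisons.

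**What to change.** In SAP 4.7 and Protocol 9.4.7, make a direct comparison the analysis of sex differences:

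1. For named contrasts (post minus pre, or one condition minus another), compare each participant's within-person value between men and women with a two-sample test. Alternatively, fit a sex-by-condition term in a repeated-measures model with participant as a random effect.
2. Report the estimated difference with a 95% CI.
3. Give sex-specific estimates with CIs as description only, and state that no sex difference will be claimed from within-sex p-values.
4. Label the analysis exploratory, state its low power, and say that a non-significant result is not evidence of no difference.
5. Amend SAP 4.9 and Protocol 9.4.9, which say no exploratory analyses are planned, to match.

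If only a description within each sex is wanted, reword the purpose in Protocol 4.1 instead. Either way, purpose and method must agree.

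**Cost.** Wording in these sections. The contrast comparison needs no new model, data or participants. The sex-by-condition option needs a repeated-measures model for the primary endpoints, where the plan now names a one-way ANCOVA. Neither option removes the power limit set by 10 per sex.
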